8.3.5. Asthma Control Questionnaire-5 (ACQ-5)

The ACQ-5 will be completed at the beginning of all study visits where the form is completed.

The ACQ-5 is a five-item questionnaire, which has been developed as a measure of subject' asthma control that can be quickly and easily completed [Juniper, 2005]. The questions are designed to be self-completed by the subject. The five questions enquire about the frequency and/or severity of symptoms (nocturnal awakening on waking in the morning, activity limitation, and shortness of breathe, wheeze). The response options for all these questions consist of a zero (no impairment/limitation) to six (total impairment/limitation) scale.

The subject should be given a quiet area in which to complete the questionnaire. The investigator should ask the subject to complete the questions as accurately as possible. If the subject requests help or clarification with any of the questions, he/she will be asked to re-read the instructions and give the answer that best reflects how he/she felt over the previous week. The subject should be reassured that there are no right or wrong answers. The investigator should not provide the subject with any answer or attempt to interpret any portion of a question.

It is recommended that the ACQ-5 be administered at the same time during each visit. To avoid biasing responses, the subjects should not be told the results of diagnostic tests prior to completing the questionnaire and should be completed before any procedures are performed on the subject to avoid influencing the subject's response. Adequate time should be allowed to complete all items on the ACQ-5.

8.4. Safety

Safety will be assessed, as indicated in the Time and Events Table [Table 3](#), by monitoring of AEs, a physical examination at screening, and vital signs (systolic and diastolic blood pressure and heart rate [pulse] at each visit. A screening 12-ECG will be conducted.

In cases of suspected pneumonia, a confirmatory chest x-ray should be conducted within 48 hours.

Planned time points for all safety assessments are listed in the Time and Events Table (Time and Events [Table 3](#)).

8.4.1. Adverse Events (AE) and Serious Adverse Events (SAEs)

The definitions of an AE or SAE can be found in [Appendix 5](#).

The investigator and their designees are responsible for detecting, documenting and reporting events that meet the definition of an AE or SAE.

8.4.1.1. Time period and Frequency for collecting AE and SAE information

- AEs and SAEs will be collected from the start of Study Treatment (the start of the run-in period) until the follow-up contact (see Section [8.4.1.3](#)), at the time points specified in the Time and Events Table [Table 3](#)).
- Medical occurrences that begin prior to the start of study treatment but after obtaining informed consent may be recorded on the Medical History/Current Medical Conditions section of the eCRF.
- Any SAEs assessed as related to study participation (e.g., protocol-mandated procedures, invasive tests, or change in existing therapy) or related to a GSK product will be recorded from the time a subject consents to participate in the study up to and including any follow-up contact.
- All SAEs will be recorded and reported to GSK within 24 hours, as indicated in [Appendix 5](#).
- Investigators are not obligated to actively seek AEs or SAEs in former study subjects. However, if the investigator learns of any SAE, including a death, at any time after a subject has been discharged from the study, and he/she considers the event reasonably related to the study treatment or study participation, the investigator must promptly notify GSK.

NOTE: The method of recording, evaluating and assessing causality of AEs and SAEs plus procedures for completing and transmitting SAE reports to GSK are provided in [Appendix 5](#).

8.4.1.2. Method of Detecting AEs and SAEs

Care will be taken not to introduce bias when detecting AEs and/or SAEs. Open-ended and non-leading verbal questioning of the subject is the preferred method to inquire about AE occurrence. Appropriate questions include:

- “How are you feeling?”
- “Have you had any (other) medical problems since your last visit/contact?”

- “Have you taken any new medicines, other than those provided in this study, since your last visit/contact?”

8.4.1.3. Follow-up of AEs and SAEs

After the initial AE/SAE report, the investigator is required to proactively follow each subject at subsequent visits/contacts. All SAEs, and non-serious AEs of special interest (as defined in Section 5.6.1) will be followed until resolution, until the condition stabilizes, until the event is otherwise explained, or until the subject is lost to follow-up (as defined in Section 6.4). Further information on follow-up procedures is given in [Appendix 5](#).

8.4.1.4. Cardiovascular and Death Events

For any cardiovascular events detailed in [Appendix 5](#) and all deaths, whether or not they are considered SAEs, specific Cardiovascular (CV) and Death sections of the eCRF will be required to be completed. These sections include questions regarding cardiovascular (including sudden cardiac death) and non-cardiovascular death.

The CV CRFs are presented as queries in response to reporting of certain CV Medical Dictionary for Regulatory Activities (MedDRA) terms. The CV information should be recorded in the specific cardiovascular section of the CRF within one week of receipt of a CV Event data query prompting its completion.

The Death CRF is provided immediately after the occurrence or outcome of death is reported. Initial and follow-up reports regarding death must be completed within one week of when the death is reported.

8.4.1.5. Regulatory Reporting Requirements for SAEs

Prompt notification by the investigator to GSK of SAEs and non-serious AEs related to study treatment (even for non- interventional post-marketing studies) is essential so that legal obligations and ethical responsibilities towards the safety of subjects and the safety of a product under clinical investigation are met.

GSK has a legal responsibility to notify both the local regulatory authority and other regulatory agencies about the safety of a product under clinical investigation. GSK will comply with country specific regulatory requirements relating to safety reporting to the regulatory authority, Institutional Review Board (IRB)/Independent Ethics Committee (IEC) and investigators.

Investigator safety reports are prepared for suspected unexpected serious adverse reactions according to local regulatory requirements and GSK policy and are forwarded to investigators as necessary.

An investigator who receives an investigator safety report describing a SAE(s) or other specific safety information (e.g., summary or listing of SAEs) from GSK will file it with the IB and will notify the IRB/IEC, if appropriate according to local requirements.

8.4.2. Asthma Exacerbations

Severe asthma exacerbations should not be recorded as an AE unless they meet the definition of an SAE (Section 13.5.2). For the purposes of this study, severe asthma exacerbations will be collected and recorded on the exacerbations log in the eCRF. The treatment details must also be recorded in the eCRF.

The time period for collection of severe asthma exacerbations will begin from the time of randomization (first receipt of investigational product) and will end after the 7-day follow-up period has been completed.

8.4.3. Pregnancy

- Details of all pregnancies in female subjects will be collected from the time the informed consent is signed (Visit 1) and until the follow up contact.
- Any pregnancy that occurs during study participation must be reported using a clinical trial pregnancy form.
- If a pregnancy is reported then the investigator should inform GSK within 2 weeks of learning of the pregnancy and should follow the procedures outlined in Section 13.6.1.
- Any SAE occurring in association with a pregnancy, brought to the investigator's attention after the subject has completed the study and considered by the investigator as possibly related to the study treatment, must be promptly reported to GSK.

8.4.4. Physical Exams

- A detailed physical examination including, but not limited to an evaluation of the lungs and cardiovascular system, will be conducted at Visit 1. Investigators should pay special attention to clinical signs related to previous serious illnesses
- Licensed practitioners who are listed on the Form 1572 are permitted to perform the physical examination. A licensed physician on the Form 1572 must sign off on the physical examinations completed by non-physicians. The results will be recorded in the subject's clinic notes. Whenever possible, the same person should perform the examination.
- If during routine clinical examination of the subject there is evidence of oral candidiasis infection, a culture can be taken and appropriate therapy should be instituted at the discretion of the Investigator.

8.4.5. Vital Signs

- Vital signs including pulse rate and systolic and diastolic blood pressure will be obtained at each clinic visit, including any Early Withdrawal visit.
- Vital signs will be obtained after subjects have rested for approximately 5 minutes in a semi-supine position, except in the case of the post exercise test vital signs which will be performed immediately following the end of the exercise test.

- At all time points where both vital signs and spirometry are performed, vital signs will be done before the spriometry measurement.
- At visits where the exercise challenge is performed, vitals will be measured before (prior to the pre-exercise spirometry) and after the exercise challenge.
- Heart rate will be measured during each exercise challenge.
- If there are any clinically significant abnormalities noted, further examinations must be performed until the abnormality is resolved.

8.4.6. *Electrocardiogram (ECG)*

- A 12-lead ECG will be performed and interpreted by the investigator or his/her suitably qualified designee at Visit 1. The ECG will be recorded after 5 minutes rest; after vital signs and prior to performing spirometry.
- Investigators will use a site ECG machine and perform a manual reading of the ECG parameters to determine whether a subject meets the eligibility criteria for enrolment in the study at screening (Visit 1).
- The ECG interpretation including the paper trace will be maintained at the site within the source documentation.

8.5. *Genetics*

Information regarding genetic research is included in [Appendix 4](#).

9. *DATA MANAGEMENT*

- For this study, subject data will be entered into GSK defined CRFs, transmitted electronically to GSK or designee and combined with data provided from other sources in a validated data system.
- Management of clinical data will be performed in accordance with applicable GSK standards and data cleaning procedures to ensure the integrity of the data, e.g., removing errors and inconsistencies in the data.
- Adverse events and concomitant medications terms will be coded using MedDRA (Medical Dictionary for Regulatory Activities) and an internal validated medication dictionary, GSKDrug.
- CRFs (including queries and audit trails) will be retained by GSK, and copies will be sent to the investigator to maintain as the investigator copy. Subject initials and full date of birth will not be collected or transmitted to GSK according to GSK policy.
- For this study subject data will be collected using GSK defined case report forms and combined with data provided from other sources in a validated data system.

- Management of clinical data will be performed in accordance with applicable GSK standards and data cleaning procedures to ensure the integrity of the data, e.g., removing errors and inconsistencies in the data.
- Adverse events and concomitant medications terms will be coded using MedDRA (Medical Dictionary for Regulatory Activities) and an internal validated medication dictionary, GSKDrug.
- Original CRFs will be retained by GSK, while the investigator will retain a copy. Subject initials will not be collected or transmitted to GSK according to GSK policy.

10. STATISTICAL CONSIDERATIONS AND DATA ANALYSES

10.1. Hypotheses

The primary endpoint is the maximal percent decrease in FEV₁ following exercise challenge at 12-hours post-dose at the end of the 2-week treatment period.

The treatment comparison is the FF/VI combination versus FP. Demonstration of efficacy for this treatment comparison will be based on a hypothesis testing approach whereby the null hypothesis is that there is no difference between treatment groups and the alternative hypothesis is that there is a difference between treatment groups.

A 2-sided 5% probability associated with incorrectly rejecting the null hypothesis (significance level) is considered acceptable for this study. In order to account for multiplicity, this primary hypothesis test on the primary endpoint for the ITT (Intent-to-Treat) population will act as a gatekeeper for all other hypothesis tests using the secondary endpoints, where these tests will proceed in a pre-defined order.

If the primary hypothesis on the primary endpoint for the ITT population is rejected then the following hierarchy of tests will be performed using the ITT population;

1. Test at the 5% level the null hypothesis that the true odds ratio between the two treatment groups of recovering to within 5% of pre-exercise FEV₁ at the 30 minute post-exercise time point following the exercise challenge at 12 hours post evening dose is equal to one.
2. Test at the 5% level the null hypothesis that the true population difference between the treatment group means in maximal percent decrease in FEV₁ from pre-exercise at 23 hrs post-dose at the end of the 2-week treatment period is zero.
3. Test at the 5% level the null hypothesis that the true odds ratio between the two treatment groups of recovering to within 5% of pre-exercise FEV₁ at the 30 minute post-exercise time point following the exercise challenge at 23 hours post evening dose is equal to one.
4. If 3 is significant then test at the 5% level the null hypothesis that the true population difference between the treatment group means in weighted mean 0-60

minutes for percentage decrease in FEV₁ from pre-exercise FEV₁ at 12 hrs post-dose at the end of the 2-week treatment period is zero.

5. If 4 is significant then test at the 5% level the null hypothesis that the true population difference between the treatment group means in weighted mean 0-60 minutes for percentage decrease in FEV₁ from pre-exercise FEV₁ at 23 hrs post-dose at the end of the 2-week treatment period is zero.

If either the primary null hypothesis or any of the above null hypotheses are not rejected, then although all of the subsequent hypothesis tests will be performed, each test result, and the associated p-value will be used for descriptive purposes only.

10.2. Study Design Considerations

10.2.1. Sample Size Assumptions

For the primary efficacy endpoint of maximal percent decrease in FEV₁ following exercise challenge at 12 hours post-dose at the end of the 2-week treatment period, given an assumed 20% screen failure rate, a 70% run-in failure rate, and a 15% withdrawal rate post-randomisation, a total of approximately 275 subjects will be screened. Given these assumed failure and withdrawal rates we expect 220 subjects will enter the run-in period, of which 66 subjects will be randomized, of which 56 subjects will be evaluable, that is completing the exercise challenges and the FEV₁ evaluations at the end of both treatment periods. With 56 evaluable subjects this study has approximately 90% power assuming a true population difference of 5% in maximal percent decrease in FEV₁ between the two treatment groups. This assumes a within-subject standard deviation (SD) of 8% where significance is declared at the two-sided 5% significance level.

Subjects will be centrally randomized to one of the two treatment sequences shown below in [Table 4](#) in a 1:1 ratio:

Table 4 Treatment Sequencing

Allocation ratio	Sequence	Period 1	Period 2
1	1	FF/VI 100/25 mcg QD via Ellipta + Placebo BD via Diskus	FP 250 mcg BD via Diskus + Placebo QD via Ellipta
1	2	FP 250 mcg BD via Diskus + Placebo QD via Ellipta	FF/VI 100/25 mcg QD via Ellipta + Placebo BD via Diskus

10.2.2. Sample Size Sensitivity

To demonstrate the sensitivity of the sample size calculation for this study, [Table 5](#) shows the effect that different within-subject standard deviations would have on the power of the study.

Table 5 Power as a function of within-subject SD

Within-subject Standard Deviation (%)	Power for the primary endpoint (%)
5	>99.9
6	99.1
7	96.0
8	90.1
9	82.3
10	73.9
11	65.7

Table 6 Sample size as a function of within-subject SD

Within-subject Standard Deviation (%)	Number of evaluable subjects
5	24
6	33
7	44
8	56
9	71
10	87
11	104

Both [Table 5](#) and [Table 6](#) assume a true population difference of 5% between the two treatment groups.

10.2.3. Sample Size Re-estimation

Blinded sample size re-estimation will be conducted when approximately 50% of the subjects have completed their second exercise challenge. In order to assess the accuracy of the sample size assumption for the within-subject SD, the linear mixed model for the primary analysis will be fitted to this blinded interim data, but with a dummy variable to denote treatment group membership. If this suggests the original assumptions behind the sample size were incorrect, an adjustment may be made to the planned number of subjects to be recruited.

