Primary Analysis Populations	
 The ITT Population will comprise all subjects randomized to treatment and who received at least one dose of trial medication. Randomized subjects will be assumed to have received trial medication unless definitive evidence to the contrary exists. This will constitute the primary population for all analyses of efficacy measures and safety measures. Outcomes will be reported according to the randomized treatment allocation. The PP Population will consist of all subjects in the ITT Population who do not have any full protocol deviations and have at least one treatment period without a partial deviation. Protocol deviations can either be full or partial. Subjects with only partial deviations in 1 treatment period will be considered part of the PP population but their data from the treatment period affected by the deviations will be excluded. The decision to exclude a subject, or part of their data, from the PP Population will be made prior to breaking the blind. This population will be used for confirmatory analyses of the primary efficacy endpoint only.

Overview	Key Elements of the RAP
Hypothesis	
Demonstration of efficacy will be based on a hypothesis testing approach, whereby the null hypothesis is that there is no difference between treatment groups for the endpoint of interest and the alternative hypothesis is that there is a difference between treatment groups
Primary Analyses	
The primary efficacy endpoint will be analysed using a mixed model repeated measures (MMRM) model allowing for fixed covariate effects of treatment, period baseline FEV₁, the mean of the two period baseline FEV₁ values, sex, age, treatment period and smoking history (number of pack years) as fixed effects, and a random intercept for each subject. The covariate-adjusted means for the primary endpoint for each treatment group will be presented together with the estimated difference between the treatment groups, a 95% confidence interval and a 2-sided p-value allowing the null hypothesis to be tested.

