2.5. Sample Size Assumptions

A total of approximately 275 subjects will be screened in order to achieve 66 randomized subjects. Allowing for a 15% withdrawal rate, this will give 56 evaluable subjects who complete the exercise challenges and the FEV₁ evaluations at the end of both treatment periods.

The sample size calculations are based on the primary efficacy endpoint of maximal percent decrease in FEV₁ following exercise challenge at 12 hours post-dose at the end of the 2-week treatment period.

With 56 evaluable subjects this study has approximately 90% power assuming a true population difference of 5% in maximal percent decrease in FEV₁ between the two treatment group means. This assumes a within-subject standard deviation (SD) of 8% where significance is declared at the two-sided 5% significance level.

A blinded sample size re-estimation will be conducted when approximately 50% of the subjects have completed their second exercise challenge. In order to assess the accuracy of the sample size assumption for the within-subject SD, the primary analysis will be run on this blinded interim data, but with a dummy variable to denote treatment group membership. If this suggests the original assumptions behind the sample size were incorrect, an adjustment may be made to the planned number of subjects to be recruited.

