7.1.2. Planned Primary Efficacy Statistical Analyses

Primary Statistical Analyses
Endpoint(s)

 Maximal percent decrease from pre-exercise FEV₁ following exercise challenge at 12 hours post evening dose at the end of the 2-week treatment period
Populations

 This analysis will be performed on both the Intent-to-Treat (ITT) and the Per Protocol (PP) populations.
Model Specification

The mixed model repeated measures (MMRM) model will include the following covariates (with example variable names): treatment (ptrtcd), sex (sex), age (age), treatment period (pernum), smoking history (supkyr: number of pack years), period baseline FEV₁ (pbli) and the mean of the two period baseline FEV₁ values (mpbli) as fixed effects, and a random intercept for each subject (subjid). A SAS procedure of the following structure will be used:
 <pre>proc mixed data=start cl nobound ; class subjid ptrtcd sex pernum ; model maxd = ptrtcd pernum pbli mpbli age sex supkyr / solution ddfm=kr ; random int / subject=subjid type=simple ; repeated pernum / subject=subjid type=simple ; lsmeans ptrtcd / diff cl e om=OMdset at (age mpbli)=(&agem. &mpblim.) ; ods output lsmeans=lsmeans ; ods output diffs=diffs ; run ;</pre>
Where OMDset is a dataset with a row for every period-subject combination that contains all of the covariates and mpblim and agem are macro variables containing the means for mpbli and age for the subjects used in the analysis. These are used to derive the adjusted means using coefficients which are based on the subjects used in the analysis.
Model Checking & Diagnostics

 Refer to Appendix 11: Model Checking and Diagnostics for Statistical Analyses.
Model Results Presentation

 The adjusted means for each treatment and the estimated treatment difference for the treatment comparison will be presented together with a 95% confidence interval for the difference and a p-value. The adjusted treatment difference and 95% confidence interval will be plotted.

Sensitivity and Supportive Statistical Analyses
Maximal Decrease (L) from Pre-Exercise FEV₁ Analysis
This supporting analysis will be analysed using a model of the same structure as described for the primary analysis.

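### Does the undefined dummy treatment variable in the blinded sample-size re-estimation put the primary 5% error rate at risk?

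*Protocol*

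**What the plan says.** Protocol 10.2.3 plans a blinded re-estimation once roughly half of the subjects have done their second exercise challenge. Its stated aim is to check the within-subject SD assumed in the sample size. To do so, the primary linear mixed model "will be fitted to this blinded interim data, but with a dummy variable to denote treatment group membership". SAP 2.5 repeats this in slightly stronger terms: "the primary analysis will be run on this blinded interim data, but with a dummy variable to denote treatment group membership".

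What follows from the result is left open. "If this suggests the original assumptions behind the sample size were incorrect", then "an adjustment may be made to the planned number of subjects to be recruited". No SD threshold, direction or cap is given.

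The planning assumptions are in Protocol 10.2.1: "With 56 evaluable subjects this study has approximately 90% power assuming a true population difference of 5" percentage points, with a within-subject SD of 8 and a two-sided 5% test. Tables 5 and 6 in Protocol 10.2.2 vary only the SD and hold the difference at 5.

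The primary model is coded in SAP 7.1.2 with the line "lsmeans ptrtcd / diff cl e om=OMdset", and its results are to be shown "together with a 95% confidence interval for the difference and a p-value". SAP 3.1 says that there is no interim analysis. SAP 3.2 places unblinding and all planned analyses after database freeze.

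**The concern.** Two different variables could be meant by the dummy.

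- **A code unrelated to allocation** (invented or re-randomised). This reveals nothing about treatment, but any real effect is absorbed into the variance, so the SD is overstated.
- **A masked code of the true allocation.** The SD is then unbiased. With only two treatments, however, masking hides only the direction. The size of the difference, its two-sided p-value and the residual SD are the same as in the unblinded fit.

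Under the second reading, running the primary analysis as SAP 7.1.2 codes it would print the p-value for the primary hypothesis at about half the planned information. The SAP synopsis describes that output as "a 95% confidence interval and a 2-sided p-value allowing the null hypothesis to be tested". No text suppresses it or limits who sees it, and N may then be changed at discretion with no adjustment of alpha. The primary test is the gatekeeper for five secondary tests at the same level, so a loss of error control here would carry through the hierarchy.

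**Working it through.** **Reproducing the planned size.** Inputs from Protocol 10.2.1: difference 5, within-subject SD 8, two-sided 5%, 56 evaluable. In a two-period crossover the treatment estimate has SE = SD × √(2/N). With N = 56 this is 8 × √(2/56) = 1.51. A noncentral t with N − 2 degrees of freedom gives 90.1% power, and 56 is the smallest N reaching 90%. The same formula returns all seven sizes in Table 6.

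**Does masking hide the p-value?** In three simulated interim data sets (28 subjects, SAP covariates, random intercept), the true code and the swapped code gave identical p-values (0.00014, 0.0005, 0.0033) and identical residual SDs. A re-randomised dummy gave 0.13, 0.98 and 0.42. So the technical point is right. With 28 completers (half of 56) the SE is 8 × √(2/28) = 2.14, and a test at the planned effect has 61% power. With 33 (half of 66) it has 69%.

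**Which reading fits the text?**

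- The protocol calls both the re-estimation and the data blinded, then introduces the dummy with a *but*. That marks the dummy as a departure from the real treatment term.
- SAP 3.2 allows unblinding only after database freeze. A masked true code would need the allocation schedule before then.
- SAP 3.1 is consistent with a variance check that shows no treatment comparison. It conflicts only with the masked-code reading.
- The aim stated in both documents is the SD. The difference, confidence interval and p-value in SAP 7.1.2 are presentation items for the final analysis.

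A code unrelated to allocation is therefore the natural reading.

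**Type I error.** Period-difference model, true difference 0, SD 8, N reset to 90% power for a difference of 5, N capped at 104 (the largest size in Table 6), final t test at a nominal two-sided 5%. The cap and the reset rule are assumptions, since the plan gives none.

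| Dummy | Use of the result | 28 completers | 33 completers |
|---|---|---|---|
| Unrelated, or no treatment term | N from SD, up or down | 5.0% | 5.0% |
| Masked true code | N from SD, increases only | 5.1% | 5.2% |
| Masked true code | N from SD, up or down | 5.5% | 5.5% |

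The small excess in the last two rows comes from reusing the interim variance estimate in the final test. It would be there even if nobody looked at the printed p-value.

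**Cost of the natural reading.** If treatment is not fitted, the within-subject variance becomes SD² + δ²/2. At δ = 5 this is 64 + 12.5 = 76.5, so the SD reads √76.5 = 8.75. At δ = 3 it is √(64 + 4.5) = 8.28, and at δ = 0 it is 8.00. Sizing for 8.75 gives 67 evaluable and 67/0.85 = 79 randomised, against 56 and 66. Averaged over simulated interims at δ = 5 with increases only, the extra is about 7 evaluable subjects compared with a masked code, and power is 93.1% against 92.8%. The error is in the safe direction for power.

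**The case for a change.** The strongest case for a change is that nothing in the text rules the masked code out. The phrase about denoting group membership, and the wish for an SD net of treatment, both lean towards it. SAP 2.5 says that the primary analysis itself will be run. If the p-value were then displayed and recruitment ended whenever it fell below 0.05, otherwise continuing to 56, the type I error would be 8.4% with 28 completers. It can also be argued that the trigger, which speaks of assumptions in the plural, takes in the 5-point difference.

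The ambiguity stands, and so does the invariance of the p-value. The large figure does not carry over to this plan. It needs the less natural reading together with a stopping rule found in neither document. It also needs nobody to be still in treatment when the look is made. Treatment, washout and second treatment take about six weeks, so some randomised subjects would still finish. With 4, 8, 14 or 20 further completers the same rule gives 6.7%, 6.1%, 5.6% or 5.3%; these numbers are an assumed range, because no recruitment rate is stated. As for the plural, the sentence refers back to one whose purpose is the SD alone.

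The trigger wording is also loose. Protocol 10.4 uses second challenge for the 23-hour test within a period, whereas the within-subject SD needs the 12-hour result from both periods. Only completion at Visit 7 makes sense, and an analyst would read it so.

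**Conclusion.** No change is needed. The documents omit a detail, but the word blinded, the stated SD purpose and the late unblinding already tell the analyst how to fill it: use a dummy unrelated to allocation or leave treatment out, and take only the SD from the fit. Done that way, the primary test keeps its 5.0% error rate, and the only cost is a cautious SD (8.75 for a true 8 at the design difference). An explicit rewrite would restate this and would keep the same upward bias. An increases-only rule would not be needed to protect alpha, since moving N in either direction also gives 5.0%.

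If a masked true code were used after all, SD-based resizing would cost 0.1 to 0.5 of a percentage point. This conclusion assumes that N is reset from the SD and not from a displayed treatment comparison, that about 28 to 33 subjects have completed both periods at the look, and that N does not exceed 104. Should the wording be touched for another reason, a sentence defining the dummy, limiting the output to the SD and naming Visit 7 would be a harmless clarification.
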